In recent years, specialty services, such as a pulmonology clinic, as well as computed tomography (CT)-scanning and novel microbiological tests have become available in Zambia, as well as other developing countries. This, in combination with the widespread availability of the high-sensitivity GeneXpert MTB/RIF test, leads us to believe that common practice of giving empiric tuberculosis treatment after a negative initial microbiological test for tuberculosis is no longer appropriate. In this study we want to explore the feasibility of an enhanced diagnostic workup for patients about to start empiric tuberculosis treatment and the impact this has on patient diagnoses and outcomes. This workup will include discussing patients in international multidisciplinary videoconferences when needed.

Societal relevance: No specific societal relevance.

Economic relevance: Might be associated with cost savings if tuberculosis treatment can be avoided, if long follow-up is avoided for self-limiting conditions and if severe conditions are diagnosed and treated in a timelier manner.

Medical relevance: Appropriate diagnosis and treatment are the cornerstone of medicine. This is in accordance with the principles of beneficence and non-maleficence. If the enhanced diagnostic workup does indeed lead to more appropriate diagnosis and treatment, this likely impacts patient quality of life and might even impact patient survival.

Other relevance: If the study findings are positive, this will justify the further building of specialty services as an addition to program-based tuberculosis services in Zambia and other developing countries.

Statement of the problem:

Tuberculosis is often diagnosed on a clinical basis, even with the widespread availability of highly sensitive laboratory tests such as GeneXpert MTB/RIF. This might lead to overtreatment of tuberculosis, as well as misdiagnosis and incorrect or delayed treatment for other respiratory diseases.

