Treatment outcomes for 2022 are as follows: 618 bacteriologically confirmed new cases of which 523 were cured (85%), 29 completed treatment, 36 died (6%), 3 failed treatment, 24 were lost to follow up, and 3 were not evaluated; 123 bacteriologically confirmed tuberculosis relapses of which 115 were

cured (93%), 5 died (4%), 2 were lost to follow up, and 1 was not evaluated; 352 clinically diagnosed new cases of which 308 completed treatment (88%), 35 died (10%), 1 failed treatment, 7 were lost to follow up, and 1 was not evaluated; 156 clinically diagnosed tuberculosis relapses of which 143 completed treatment (92%), 9 died (6%), and 3 were lost to follow up.

The other first-level hospitals had somewhat lower numbers of patients in 2023.

Intervention: All included patients will undergo the study intervention. Participants will be included from the tuberculosis clinic at first-level hospitals. They will be reviewed by one of the study physicians prior to initiating empiric tuberculosis treatment. A full history and physical examination will be taken and available results will be reviewed (laboratory results, sputum results, and chest X-ray). Depending on the results, appropriate measures will be taken there, including possible treatment with antibiotics or a wait-and-see approach for suspected viral infections. If further diagnostics are deemed to be indicated, a patient will be referred to the pulmonology clinic at University Teaching Hospital in Lusaka, Zambia. There, appropriate additional diagnostics will be requested, including additional blood tests (such as aspergillus serology), repeat chest X-ray, spirometry, CT-scan of the chest (if no other clear clinical diagnosis), bronchoscopy (if indicated based on CT-scan) and sputum and/or bronchial washing bacterial and mycobacterial cultures. The empiric treatment will be withheld initially if the study investigator thinks that an alternative diagnosis is more likely, while awaiting the additional investigations. If the study investigator thinks it is in the interest of the patient, then empiric tuberculosis treatment will be initiated while awaiting the results for the additional investigations. When a final diagnosis is made, appropriate treatment decisions will be made. If a clear diagnosis cannot be made locally, patients will be discussed in a multidisciplinary team meeting between St. Antonius Hospital and University Teaching Hospital.

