Methods: Participants will be asked to participate in the study once the clinician at the first-level hospital has decided to start empiric tuberculosis treatment. If the patients provide written informed consent, they will be reviewed by the study physician on-site, and possibly referred for further investigations as described above. Quality of life will be assessed at baseline, as well as during follow up. Patients will be followed up for 6 months, at which time every patient file will be reviewed by a study investigator and the final diagnosis will be determined.

Primary outcome: diagnosis at 6 months (tuberculosis versus alternative diagnosis)

Secondary outcomes: quality of life at 6 months (EUROHIS-QOL), change in quality of life from baseline to 6 months (EUROHIS-QOL), survival at 6 months, number of patients that received tuberculosis treatment, number of patients that had side effects attributed to tuberculosis treatment,

Number of patients to include: 300

Sample size calculation: The power is set at 80% and α at 0.05. Assuming a 10% mortality in the historic control group (based on 2022 tuberculosis outcome data from Chawama first-level hospital), and a 5% mortality in the intervention group, 238 patients will have to be included. A safety margin of 20% of refusal to participate in the study and loss to follow up is assumed, so that approximately 300 patients will have to be included.

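### The six-month diagnosis may be set by the same investigator who chose the work-up and withheld or started treatment, leaving the primary proportion open to self-confirmation bias of unknown size

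*Combined protocol and SAP*

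**What the plan says.** The Primary outcome entry has two categories at six months: tuberculosis, or an alternative diagnosis. Methods says how the label is assigned: "every patient file will be reviewed by a study investigator and the final diagnosis will be determined". No second reader, separation from patient care, masking or criteria for either label are stated.

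The Intervention section describes the earlier decisions:

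- First contact: "They will be reviewed by one of the study physicians prior to initiating empiric tuberculosis treatment".
- Further tests are selective: "If further diagnostics are deemed to be indicated, a patient will be referred to the pulmonology clinic".
- Withholding treatment: "The empiric treatment will be withheld initially if the study investigator thinks that an alternative diagnosis is more likely".
- Starting treatment while results are pending: "If the study investigator thinks it is in the interest of the patient, then empiric tuberculosis treatment will be initiated".
- Shared decision: "If a clear diagnosis cannot be made locally, patients will be discussed in a multidisciplinary team meeting".

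The Background states the team's prior view. The availability of specialty services, CT and GeneXpert "leads us to believe that common practice of giving empiric tuberculosis treatment after a negative initial microbiological test for tuberculosis is no longer appropriate".

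Under Statistical analysis, the share of alternative diagnoses is reported descriptively. The historic control group is named as a comparison for survival, not for the diagnosis.

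**The concern.** Everyone enrolled has a negative initial sputum GeneXpert, and not everyone goes on to further tests. Some final labels will therefore rest largely on clinical judgement. The plan uses the same role name, study investigator, for the person who decides on treatment and for the person who sets the final diagnosis, and it does not separate the two. Someone who withheld treatment because tuberculosis seemed unlikely could later decide whether that was right. Someone who started treatment could do the same in the other direction.

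The primary result is a single proportion with no comparator, so a lean in doubtful files passes straight into the estimate. A confidence interval, if one were added, would reflect sampling error only. A tuberculosis programme asked to act on the result could fairly discount it as self-assessment.

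**Working it through.** **1. The plan's own figure.** The only sample size calculation is for mortality, a secondary outcome: 10% historic against 5%, 80% power, α 0.05. A one-sample, two-sided test against a fixed 10% gives

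n = [(1.960 × √(0.10 × 0.90) + 0.842 × √(0.05 × 0.95)) / 0.05]² = 238.03,

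which matches the stated 238. Then 238 / 0.80 = 297.5, or approximately 300. No precision target is given for the diagnosis outcome, so I use both 300 and 238 as denominators.

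**2. Who decides what.**

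| Step | Section | Decided by |
|---|---|---|
| First review | Intervention | one of the study physicians |
| Withhold or start treatment while results are pending | Intervention | the study investigator |
| Multidisciplinary discussion | Intervention | two hospitals, only if no clear local diagnosis |
| Final diagnosis (primary outcome) | Methods | a study investigator |

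Nothing requires the last row to be a different person from the first two. The meeting is triggered by doubt, so a confident first call need never reach it. The text permits one person to do both tasks; it does not say that this happens.

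**3. Sampling error as a yardstick.** Half-width = 1.96 × √(p(1 − p)/n).

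| True rate p | n = 300 | n = 238 |
|---|---|---|
| 50% | 5.7 points | 6.4 points |
| 80% | 4.5 points | 5.1 points |

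**4. Effect of mislabelling.** A net 15 of 300 files moved one way is 15/300 = 5.0 points. To see what that requires, let fp be the share of true tuberculosis labelled alternative, and fn the share of true alternatives labelled tuberculosis. Then

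observed rate = p(1 − fn) + (1 − p)fp, and bias = (1 − p)fp − p·fn.

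The values p = 60% and 80% come from the Background's conjecture about inappropriately treated patients. The error rates are my assumptions.

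| fp | fn | Bias at p = 60% | Bias at p = 80% |
|---|---|---|---|
| 10% | 0 | +4 | +2 |
| 20% | 0 | +8 | +4 |
| 30% | 0 | +12 | +6 |
| 0 | 10% | −6 | −8 |
| 10% | 10% | −2 | −6 |

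At p = 60%, 300 patients include 120 with true tuberculosis, so a net upward shift of 15 files needs 15/120 = 12.5% of them mislabelled and no errors the other way. At p = 80% it needs 15/60 = 25%.

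**5. Direction.** Bias is upward only if (1 − p)fp > p·fn. That means fp > 1.5 × fn at p = 60%, and fp > 4 × fn at p = 80%. The documents give neither error rate.

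**The case against.** **The documents do not show a direction.** A reader might infer that the design inflates the alternative-diagnosis rate. The stated belief in the Background makes that plausible, but the Intervention section lets the investigator start treatment as well as withhold it, and self-confirmation can follow either choice. Selective testing can also miss alternatives. This objection stands.

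**The premise rests on silence.** A reader might also infer that one person always does both tasks. The plan only leaves this open.

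**The size is hypothetical.** Fifteen files is an assumed count. A bias of 5 to 10 points would require 5 to 10% of all files to be mislabelled, net, in the same direction, and nothing in the documents supports that. The plan also mentions no confidence interval for this outcome, so the half-width is only a yardstick. Both points stand.

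**Doubtful files already have a route.** The multidisciplinary meeting is a real safeguard, but a partial one. Local clinicians decide who reaches it, and it is not described as masked.

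**Physician judgement is part of what is being measured.** The primary objective concerns what an experienced pulmonary physician can diagnose. That justifies a judged outcome. It does not require the physician who made the initial decisions to set the final label, and Methods already makes the six-month review a separate step.

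**Changing the reviewer has limits.** Treatment and tests are visible in the file, so full masking is impossible. Colleagues may share the team's belief. The absence of written criteria for the two labels is a separate gap that this change does not close. All three limits stand, but self-confirmation by the managing physician would still be removed.

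**Conclusion.** The concern holds in a limited form. The plan allows the person who chose the work-up and withheld or started treatment to set the primary outcome, and the only shared decision is reached when local clinicians are unsure. The alternative-diagnosis rate is therefore open to self-confirmation bias of unknown size, plausibly upward and possibly downward.

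Under the assumed error rates above, the shift can match or exceed sampling error, but those rates are illustrative. The documents do not support a statement that the rate is biased upwards, or any particular number of points. The change is worth making because the outcome is primary and uncontrolled and the cost is small. The sample size is unaffected.

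**What to change.** In Methods, state that the planned six-month file review is done by a study investigator who did not review or manage that patient. The reviewer records tuberculosis or alternative diagnosis from the clinical data and test results before reading the first physician's stated opinion. Acknowledge that full masking is not possible because treatment is visible in the file. Files that the reviewer cannot classify clearly go to the existing multidisciplinary meeting.

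Do not report concordance between the baseline working diagnosis and the final diagnosis as reader agreement. The second is made with more information, so a difference may be proper revision, which is the purpose of the work-up.

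The cost is a rota among existing investigators, some meeting time and some loss of familiarity with the patient. Patient care does not change, and no file is routinely read twice. This assumes at least two study physicians, as the Intervention section's wording implies. Methods refers to the on-site study physician in the singular and no head count is given for the four hospitals, so the sponsor should confirm that files can be exchanged, between sites if necessary.

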Research question: does an enhanced diagnostic workup for patients about to start empiric tuberculosis treatment in Lusaka, Zambia, lead to alternative diagnoses and improved patient outcomes after six months?

Primary objective: to determine in what proportion of patients who are about to start empiric tuberculosis treatment, an alternative diagnosis can be made through the use of a concise additional workup by an experienced pulmonary physician, including review of available data, as well as additional laboratory, functional, and imaging investigations

Secondary objectives: to determine whether establishing and treating alternative diagnoses in patients who were about to start empiric tuberculosis treatment leads to improved quality of life and survival after six months

In- and exclusion criteria: All adult patients who have a negative initial GeneXpert MTB/RIF test on sputum, but are about to start standard first-line treatment for suspected pulmonary tuberculosis on clinical grounds (i.e. empiric tuberculosis treatment), at four first-level Hospitals in Lusaka, Zambia. Patients will be excluded if they are inpatients (due to suspected tuberculosis).

Number of eligible patients per year: Estimated 410 eligible patients per year in Chawama (450 clinically diagnosed pulmonary tuberculosis patients at Chawama first-level hospital in 2023, including children). The total population at Chawama first-level hospital in 2023 included 5361 presumptive tuberculosis cases, of whom 5270 had GeneXpert MTB/RIF testing done, and of whom 426 had a positive result from GeneXpert MTB/RIF. There is a discrepancy with the number of bacteriologically confirmed tuberculosis cases, which is reported at 663 for the year. The reason for this is not entirely clear, but might be due to additional testing being performed at different facilities, and the use of other tests for diagnosing tuberculosis, such as lipoarabinomannan assay and acid-fast bacilli smear. Interestingly, the percentage of patients who had a tuberculosis relapse was higher in patients being treated empirically than in patients with bacteriologically confirmed tuberculosis (107 out of 450 (24%) versus 107 out of 663 (16%)).

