Statistical analysis: Descriptive statistics will be used to describe percentage of alternative diagnoses, as well as percentage of patients that has quality of life scores indicating they are not satisfied or very dissatisfied, the percentage of patients who received tuberculosis treatment and the percentage of patients that had side effects attributed to tuberculosis treatment. Paired analyses will be used to compare quality of life at baseline and during follow up. Multivariate regression analyses will be used to identify what factors associate with quality of life and survival. We will use per-protocol analysis methods for the primary analyses, with intention-to-treat analyses as a secondary tool. We will use a historic control group of patients who underwent empiric TB treatment at the study sites in the year prior to the study as a comparison for survival. Additionally, as data for the tuberculosis clinic are collected in a standard fashion, it will be able to compare the number of patients being referred to the clinic, the number of patients receiving treatment for bacteriologically confirmed tuberculosis, and the number of patients receiving empiric tuberculosis treatment, as well as treatment outcome data, between the study period and the period prior to and after the study.

Burden and risks for participants: The burden for the participants consists of having to travel to University Teaching Hospital (4.2 km – 10.6 km distance) for review and potential additional investigations that cannot be done on the same day (CT-scan and bronchoscopy). The additional investigations might necessitate venepuncture (slightly painful, low risk of hematoma or bleeding), chest X-ray (low dose radiation (0.1mSv)), spirometry (low risk of feeling uncomfortable), and

potentially CT-scan of the chest (medium dose radiation (6.1 mSv)), and bronchoscopy (discomfort for most patients, risk of serious complications (e.g. bleeding, pulmonary oedema, pneumothorax) ca. 1%). It needs to be emphasized that these investigations would be considered as the standard-of-care in a high-resource setting, and, in that sense, are not actually an additional burden at all.

Study duration: 16 months

Start date: 1/12/2024

Final inclusion: 31/12/2025

End date: 30/06/2026

Dissemination plan:

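### The 10% control mortality fits only new clinically diagnosed cases; with relapses counted the 2022 data give 8.7%, and power against 5% is 52% to 65%, not 80%

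*Combined protocol and SAP*

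**What the plan says.** The Sample size calculation sets power at 80% and α at 0.05. It continues "Assuming a 10% mortality in the historic control group (based on 2022 tuberculosis outcome data from Chawama first-level hospital"), takes 5% for the intervention group, and arrives at 238 patients. It then adds an allowance: "A safety margin of 20% of refusal to participate in the study and loss to follow up is assumed". This leads to "Number of patients to include: 300".

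The 2022 Chawama outcomes, given after the paragraph on eligible patients per year, list the two clinically diagnosed groups separately: "352 clinically diagnosed new cases of which 308 completed treatment (88%), 35 died (10"%), and "156 clinically diagnosed tuberculosis relapses of which 143 completed treatment (92%), 9 died (6%), and 3 were lost to follow up".

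The In- and exclusion criteria cover all adults with a negative initial GeneXpert who are about to start empiric first-line treatment. The only exclusion is: "Patients will be excluded if they are inpatients (due to suspected tuberculosis"). The estimate of 410 eligible patients per year starts from "450 clinically diagnosed pulmonary tuberculosis patients at Chawama first-level hospital in 2023, including children", of whom 107 were relapses. The Statistical analysis section compares survival with a "historic control group of patients who underwent empiric TB treatment at the study sites in the year prior to the study".

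**The concern.** The 10% describes only part of the population that will be enrolled and compared. Relapses meet the entry criteria as written, belong to the historic control group as defined, and had lower recorded mortality. They are not a small fraction: 156/508 = 31% of clinically diagnosed patients in 2022 and 107/450 = 24% in 2023. Leaving them out raises the planning rate, widens the assumed difference from 5%, and makes the required number look smaller.

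Survival is a secondary outcome, but it is the only outcome behind the sample size. The 10% does not enter the analysis, which uses the observed prior-year cohort. What is at stake is the stated power, and so how a survival result showing no difference would be read. A reader told that the comparison had 80% power would take such a result as stronger evidence against a benefit than it is.

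**Working it through.** **Inputs.** α = 0.05, power 80%, 10% against 5%, and the 20% margin come from the Sample size calculation. The death counts are the 2022 Chawama outcomes. The plan names no formula and no sidedness.

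**Reproducing 238.** The two-sided one-sample formula against a fixed rate is

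n = [1.96·√(p0(1−p0)) + 0.8416·√(p1(1−p1))]² / (p0−p1)²

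With p0 = 0.10 and p1 = 0.05: (1.96 × 0.3000 + 0.8416 × 0.2179)² / 0.05² = 238.0. This matches. A two-sided two-sample formula would give 435 per group. The margin is 238/0.8 = 298, stated as about 300.

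**Control rate from the plan's data.**

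- New cases: 35/352 = 9.94%.
- Relapses: 9/156 = 5.77%.
- Together: 44/508 = 8.66%, Wilson 95% interval 6.5% to 11.4%.
- Without a recorded outcome: 7 + 1 among new cases and 3 + 1 among relapses (the relapse outcomes sum to 155 of 156), so 12/508 = 2.4%. Among the rest, 44/496 = 8.87%.

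**Power with the same formula.**

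Power = Φ{[(p0−p1)√n − 1.96·√(p0(1−p0))] / √(p1(1−p1))}

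For p0 = 0.0866, p1 = 0.05, n = 238: (0.0366 × 15.43 − 1.96 × 0.2813)/0.2179 = 0.06, so the power is 52%. The column for 293 is 300 less the register's 2.4% without an outcome.

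| Effect, control rate 8.66% | 238 | 293 | 300 | n for 80% |
|---|---|---|---|---|
| Stated 5% | 52% | 64% | 65% | 403 |
| Halving, to 4.33% | 72% | 82% | 84% | 279 |
| Five-point drop, to 3.66% | 88% | 95% | 95% | 202 |

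Exact two-sided binomial power against 5% is 59%, 60% and 67% (rejecting at no more than 12, 15 and 16 deaths). For the halving it is 77%, 79% and 84%. The plan's own 10% against 5% at 238 gives 79% by the same exact test. The normal approximation is therefore not the cause of the shortfall.

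**Sensitivity of power against 5%.**

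| Control rate | Basis | 238 | 300 |
|---|---|---|---|
| 6.5% | lower end of interval | 13% | 16% |
| 8.9% | recorded outcomes only, 44/496 | 57% | 70% |
| 9.0% | 2023 mix: (107/450) × 5.77% + (343/450) × 9.94% | 59% | 72% |
| 9.5% | assumed adult share 410/450, no child died: 44/462.8 | 71% | 83% |
| 9.7% | the same, recorded outcomes only: 44/451.9 | 75% | 86% |
| 11.4% | upper end of interval | 96% | 99% |

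**Break-even.** For 80% power against 5%, the control rate must be at least 10.0% at 238 evaluable patients and 9.4% at 293 or 300. At 8.66%, the mortality detectable with 80% power is 4.0%, 4.4% and 4.5% at 238, 293 and 300.

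**Uncertainty in the controls.** All the powers above treat the control rate as known, as the formula behind 238 does. If the historic cohort is assumed to have 508 patients at 8.66% and is compared by a two-sample test, power against 5% falls to about 42% at 238 and 49% at 300.

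**The case against.** The strongest reply is that 8.7% is not the rate in the trial's population either. The 2022 counts state neither age nor inpatient status, they come from one of four sites, and the 2023 count is known to include children. Under the adult assumption (9.5% to 9.7%), 80% is reached if all 300 patients are evaluable.

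Nor do the data contradict 10%. The interval includes it, 44 or fewer deaths in 508 has probability 0.18 if the true rate is 10%, and the difference between new cases and relapses is not significant (Fisher p = 0.17).

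Finally, 10% to 5% is also a halving and a five-point drop. Holding 5% fixed while lowering the control rate is the least favourable of the three readings.

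Much of this stands as a limit on precision. The 52% and 65% depend on the 8.7% and on the stated 5%, and the fault lies in a planning input, not in the arithmetic. It does not rescue the 10%. The plan attributes that figure to these data, and the data give 10% only when relapses are left out. The same interval that includes 10% also reaches 6.5%. The adult figures are upper-end assumptions, because they require that no child died, and they still fall short of 80% at 238. Removing inpatients could move the rate either way. The plan states a target rate of 5%, not a ratio or a difference.

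**Conclusion.** The concern holds. The 10% is not what the plan's own data give for the patients it will enrol and compare; counting relapses gives about 8.7%. At that rate, against the stated 5%, power is 52% at 238 evaluable patients and 65% at 300, so the claimed 80% is not reached even with complete follow-up. The chance of missing a true 5% is then 35% to 48%, not 20%.

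This rests on three assumptions: that the 2022 mix of new and relapse cases at Chawama approximates the eligible population, that 5% is the intended target, and that the control rate is treated as known. Relaxing the first could move power in either direction. Replacing the second by a halving brings 80% within 300. Relaxing the third lowers power. The descriptive primary outcome and the planned survival analysis are not affected; only the stated power is.

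**What to change.** Rewrite the sample size paragraph as follows.

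1. Base the control mortality on new plus relapse clinically diagnosed patients, restricted to adult outpatients where the register allows, and report the rate with its interval.
2. State whether the intended effect is a fixed 5% or a halving.
3. State how many of the 300 are expected to be evaluable. The 20% margin mixes refusal, which happens before inclusion, with loss to follow-up, so the plan leaves this number open.
4. Restate the power, or the detectable mortality, across 238 to 300 evaluable patients.

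The cost is one register tabulation and some rewording. No patients need to be added; the price is a less favourable stated power for survival.

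### The 238 patients for 80% power match a formula that treats 10% control mortality as known, but survival will be compared with a finite historic group; under a two-sided pooled test 238 evaluable patients give about 71-75%

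*Combined protocol and SAP*

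**What the plan says.** All references are to the combined protocol and SAP.

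- **Sample size calculation.** Power is 80% and alpha 0.05. Mortality is taken as 10% in the historic controls, from 2022 outcomes at Chawama, "and a 5% mortality in the intervention group, 238 patients will have to be included". Then "A safety margin of 20% of refusal to participate in the study and loss to follow up is assumed", which brings the total to about 300. No formula, test, sidedness or number of controls is stated.
- **Number of patients to include.** "Number of patients to include: 300".
- **Statistical analysis.** "We will use a historic control group of patients who underwent empiric TB treatment at the study sites in the year prior". The size of this group is not given.
- **Methods.** Consent comes before study review: "If the patients provide written informed consent, they will be reviewed by the study physician on-site".
- **Counts that bear on the control group.** For 2023, "450 clinically diagnosed pulmonary tuberculosis patients at Chawama first-level hospital in 2023, including children". For 2022 at the same hospital, "352 clinically diagnosed new cases of which 308 completed treatment" and "156 clinically diagnosed tuberculosis relapses of which 143 completed treatment". There are four sites, and the other hospitals are described as having had somewhat fewer patients in 2023.

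Survival at 6 months is a secondary outcome. The primary outcome, diagnosis at 6 months, is analysed descriptively.

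**The concern.** The calculation and the analysis appear to describe two different comparisons. One sets the study patients against a fixed 10%. The other sets them against a sample of earlier patients, so the control mortality carries its own sampling error. If that error was left out, 238 evaluable patients do not give 80% power under an ordinary two-sided test.

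The mortality calculation is the only basis offered for the size of the trial, and survival is named in the secondary objectives. A survival result that is not significant would be read against a stated 80% power that may not have been available.

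A second uncertainty adds to the first. The 20% margin combines refusal with loss to follow-up. Refusal happens at consent, before a patient is enrolled; loss happens afterwards. A reader cannot tell how many of the 300 are expected to be evaluable.

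**Working it through.** **Inputs from the plan.** Control mortality p0 = 0.10, study mortality p1 = 0.05, alpha 0.05, power 80%, stated n = 238, inclusion 300, margin 20%.

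**Step 1: reproduce 238.** One-sample test against a fixed 10%, two-sided:

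n = [1.960 × √(0.10 × 0.90) + 0.8416 × √(0.05 × 0.95)]² / 0.05² = [0.5880 + 0.1834]² / 0.0025 = 238.03.

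Other standard set-ups give different numbers: one-sample one-sided 183; two-sample 1:1 two-sided 435 per group; two-sample 1:1 one-sided 343 per group. One other set-up does match: a one-sided pooled two-sample test with three controls per patient (238 against 714) has power 0.800. The plan states neither one-sided testing nor a 3:1 ratio.

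The margin also reproduces: 238 / 0.8 = 297.5, or about 300; and 300 × 0.8 = 240.

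**Step 2: number of controls (assumption).** The plan gives no count for the year before the study. Chawama had 352 + 156 = 508 clinically diagnosed cases in 2022 and 450 in 2023. Four times these is 2032 and 1800. Because the other sites were smaller, these are ceilings. A total of 1000 means the other three average (1000 − 450)/3 ≈ 183, or 41% of Chawama's 450. A total of 1300 means (1300 − 450)/3 ≈ 283, or 63%. The range used is 1000-2032; 1300-1800 fits the plan's description best.

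**Step 3: evaluable patients (assumption).** In the 2022 Chawama data, 7 + 1 + 3 = 11 of 508 clinically diagnosed patients were lost or not evaluated. Applied to 300: 300 × (1 − 11/508) = 293.5, or about 293. If the whole 20% margin comes out of the 300, 240 remain.

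**Step 4: power of a two-sided pooled two-sample test.** With n1 study patients and n0 controls,

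power = Φ{ [0.05 − 1.960 × s0] / s1 }, where s0 = √[p̄(1 − p̄)(1/n1 + 1/n0)], s1 = √[p1(1 − p1)/n1 + p0(1 − p0)/n0] and p̄ is the weighted mean mortality.

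For n1 = 238 and n0 = 1000: p̄ = (11.9 + 100)/1238 = 0.0904, s0 = 0.02068, s1 = 0.01702. Then (0.05 − 0.04053)/0.01702 = 0.556, and Φ = 0.711.

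The table gives the formula result, with exact binomial enumeration of the same test in brackets.

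| Controls | 238 evaluable | 240 evaluable | 293 evaluable | Evaluable needed for 80% |
|---|---|---|---|---|
| 1000 | 71.1% (72.3%) | 71.5% (72.8%) | 79.3% (80.1%) | 299 (293) |
| 1300 | 72.9% (74.1%) | 73.3% (74.3%) | 81.4% (82.1%) | 283 (277) |
| 1800 | 74.7% (75.7%) | 75.1% (75.9%) | 83.4% (83.9%) | 269 (266) |
| 2032 | 75.3% (76.1%) | 75.7% (76.5%) | 84.0% (84.4%) | 265 (262) |

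**Step 5: other tests at 238 evaluable, 1000-2032 controls.**

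- Fisher's exact, two-sided: 70-75%.
- Likelihood-ratio, two-sided: 76-80%.
- Unpooled Wald, two-sided: 81-85%, but its null rejection rate is 5.4-5.6% overall, and 3.7-4.0% in the direction of benefit against a nominal 2.5%.
- Pooled, one-sided: 83-86%.

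**The case against.** The strongest reply is that the trial will include 300 patients, not 238. With about 293 evaluable, exact power of the pooled test is at least 80% throughout the assumed control range; the dip to 79% with 1000 controls is a feature of the normal approximation. This stands. The shortfall appears only if losses after enrolment are substantial. But the plan does not make this argument: it attaches 80% to 238 and does not say how much of its margin is loss after enrolment.

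A second reply is that the test is unspecified, and some choices exceed 80% at 238. That also stands for a one-sided or unpooled Wald test, and a Schoenfeld approximation for a log-rank test gives 85-90%. That approximation is rough here, being derived for hazard ratios near 1. The dependence on the test is a reason to name it.

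Three stronger readings are tempting and are not supported:

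- *That the plan is shown to have ignored control-group error.* This is inferred from a matching number. The one-sided 3:1 design also gives 238, so it is the likely explanation, not a documented one.
- *That power is only about 65%.* That figure takes Chawama's 508 cases from 2022 as the whole control group. The plan draws controls from all study sites in the year before a December 2024 start, so it is neither the right sites nor the right year.
- *That the trial is underpowered and must enrol more.* With 300 enrolled and small losses, the target is roughly met.

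**Conclusion.** The point holds in a modest and conditional form. The stated 80% at 238 corresponds to a comparison with a known 10%, while the planned comparison is with a finite group. Under a two-sided pooled test, 238 evaluable patients fall short by roughly 4 to 9 percentage points over the whole assumed range of controls. With 300 enrolled, the result runs from about 71% (1000 controls, full 20% margin lost) to about 84% (2032 controls, about 2% lost).

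This rests on the plan's own 10% and 5%, an assumed 1000-2032 controls, two-sided testing, and the assumed evaluable numbers. It concerns a secondary outcome. It is worth correcting because this calculation is the sole justification for the sample size and the correction is cheap.

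**What to change.** Rewrite the sample size paragraph as a two-sided two-sample comparison with unequal groups. State:

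1. the test to be used for survival against the historic group;
2. the expected number of historic controls over the four sites, from the clinics' routine data;
3. the expected evaluable patients out of 300, with refusal before enrolment separated from loss to follow-up;
4. in place of 80% at 238, the power over that range, or the study mortality detectable with 80% power. By the pooled formula with 1000-2032 controls, the latter is about 4.6-4.8% with 238 evaluable and 5.0-5.2% with 293.

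In the Statistical analysis section, add that the mortality difference will be reported with a confidence interval that includes the control group's sampling error.

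The cost is a reworded paragraph, one or two added sentences and a count of controls. Enrolment can stay at 300, provided the sponsor accepts that the stated power may fall below 80% if losses are substantial. Procedures and the primary outcome do not change.
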